3.3.4.1 Discontinuation of trial treatment

An individual patient will discontinue trial treatment if:

- The patient wants to discontinue trial treatment, without the need to justify the decision.
- The patient has repeatedly shown to be non-compliant with important trial procedures and, in the opinion of both, the investigator and sponsor representative, is not willing or able to adhere to the trial requirements in the future.
- The patient can no longer receive trial treatment for medical reasons (such as surgery, adverse events, other diseases, or pregnancy). The subject shows an elevation of AST and/or ALT ≥3-fold upper limit of normal (ULN) combined with an elevation of total bilirubin ≥2-fold ULN (measured in the same blood sample) and/or needs to be followed up according to the 'DILI checklist' provided in the ISF.
- The subject experiences an infection with SARS-CoV-2 (as confirmed by PCR Test, see Section 5.2.3) or an infection other than pulmonary exacerbation which requires systemic antibiotic treatment. In case a patient needs to take concomitant medication that interferes

with the investigational medicinal product or other trial treatment (see Section 4.2.2), it will be decided on a case-by-case basis after consultation with the Sponsor whether or not discontinuation of trial treatment is required.

If new efficacy/safety information becomes available, Boehringer Ingelheim will review the benefit-risk-assessment and, if needed, pause or discontinue the trial treatment for all patients or take any other appropriate action to guarantee the safety of the trial patients.

Boehringer Ingelheim		22 Apr 2021
BI Trial No.: 1405-0008		
c31693972-02	Clinical Trial Protocol	Page 52 of 111

Even if the trial treatment is discontinued, the patients remain in the trial and, given their agreement, will undergo the procedures for early treatment discontinuation and follow-up as outlined in the Flow Chart and Section 6.2.3.

Additional patients may be recruited, if early treatment discontinuation is due to non-safety related reasons (e.g. unable to continue protocol defined visits due to personal reason), or due to COVID-19 given the prevalence of the coronavirus in the community. In all cases, recruitment of additional patients should only occur if the patient discontinued treatment prior to week 12, and must first be discussed and agreed upon with the sponsor.

3.3.4.2 Withdrawal of consent to trial participation

Patients may withdraw their consent to trial participation at any time without the need to justify the decision.

If a patient wants to withdraw consent, the investigator should be involved in the discussion with the patient and explain the difference between trial treatment discontinuation and withdrawal of consent to trial participation, as well as explain the options for continued follow-up after trial treatment discontinuation, please see Section 3.3.4.1 above.

3.3.4.3 Discontinuation of the trial by the sponsor

Boehringer Ingelheim reserves the right to discontinue the trial overall or at a particular trial site at any time for the following reasons:

- Failure to meet expected enrolment goals overall or at a particular trial site.
- New efficacy or safety information, toxicological findings or serious adverse events invalidating the earlier positive benefit-risk-assessment, please see Section 3.3.4.1.
- Deviations from GCP, the trial protocol, or the contract impairing the appropriate conduct of the trial.
- The sponsor decides to discontinue the further development of the investigational product.

Further follow up of patients affected will occur as described in Section 3.3.4.1. The investigator / the trial site will be reimbursed for reasonable expenses incurred in case of trial termination (except in case of the third reason).

3.3.5 Replacement of patients

Patients with premature treatment discontinuation will not be replaced as all safety data captured from treated patients will be evaluated. In certain cases of premature treatment discontinuation, the recruitment of additional patients may be considered, see Section 3.3.4.1 for details.

Page 53 of 111

Proprietary confidential information © 2021 Boehringer Ingelheim International GmbH or one or more of its affiliated companies

4. **TREATMENTS**

4.1 INVESTIGATIONAL TREATMENTS

The investigational products used in this trial, BI 1323495 and placebo, are manufactured by Boehringer Ingelheim Pharma GmbH & Co. KG.

4.1.1 Identity of the Investigational Medicinal Products

Film-coated tablets of 2 dosage strengths and matching placebo tablets were developed for oral administration: 10° mg (14 x 6.8 mm oval) and 50° mg (11 x 5.5 mm oval.

Substance:	BI 1323495
Pharmaceutical formulation:	Film-coated tablets
Source:	Boehringer Ingelheim Pharma GmbH & Co. KG
Unit strength:	10 mg or 50 mg
Posology:	bid for 12 weeks in Part A and qd for 12 weeks in Part B
Method and route of administration:	Oral, as tablets

Table 4.1.1: 1 Test product BI 1323495

Further details are given in the Investigator's Brochure [c21238478-05].

Matching placebo tablets have been developed, containing mannitol, microcrystalline cellulose, and magnesium stearate.

Page 54 of 111

Proprietary confidential information © 2021 Boehringer Ingelheim International GmbH or one or more of its affiliated companies

Substance:	No substance (placebo)
Pharmaceutical formulation:	Film-coated tablets
Source:	Boehringer Ingelheim Pharma GmbH & Co. KG
Unit strength:	No strength, matched to active test drug
Posology:	bid for 12 weeks in Part A and qd for 12 weeks in Part B
Method and route of administration:	Oral, as tablets

The clinical trial supplies will be provided in blisters. The tablets should be handled according to the labelled storage instructions and shelf life.

4.1.2 Selection of doses in the trial and dose modifications

The 30 mg bid dose of BI 1323495 is a confirmed safe and tolerated dose after multiple dosing in healthy volunteers and could potentially be a therapeutic dose that is applicable for both, EMs and PMs, and will thus be tested in Part A. In the MRD trial 1405-0002, with 30 mg bid in EMs, median trough NE inhibition at steady state exceeded 90% which is considered a PD effect size potentially associated with a clinical benefit if maintained long term (Table 1.2.3.2: 1). The 150 mg qd dose of BI 1323495 selected for Part B was based on safety/tolerability data from higher dose groups of the healthy volunteer MRD study and is anticipated to reach the maximal safely achievable PD effect. This dose was selected to ensure that exposures will not exceed a gMean value that was observed and safely tolerated in the MRD trial 1405-0002, and to not exceed exposure boundaries that were predefined based on animal toxicity studies (see Section 1.2.2.4). Doses will be administered with food containing a fat component.

4.1.3 Method of assigning patients to treatment groups

After the assessment of all in- and exclusion criteria, each eligible patient will be randomised to treatment groups according to a randomisation plan in a 3:1 ratio at visit 3 via Interactive Response Technology (IRT). Note that the medication number is different from the patient number (the latter is generated during screening via the IRT System).

4.1.4 Drug assignment and administration of doses for each patient

The treatments to be evaluated are outlined in Table 4.1.4: 1 below. The number of units for placebo corresponds to the number of units of the respective dose group of the active substance.

Trial medication will be dispensed in a double-blinded manner to patients. That means, investigators and patients will not know if a patient is assigned to BI 1323495 or placebo.

Treatment	Substance	Formulation	Unit strength	Dosage	Total daily dose
Part A	BI 1323495	Tablet, film coated	10 mg	3 tablets bid	60 mg
Part B	BI 1323495	Tablet, film coated	50 mg	3 tablets qd	150 mg

 Table 4.1.4: 1 Dosage and treatment schedule for the treatment phase

Subjects should take the study drug while in a standing or sitting position, as an oral dose together with about 240 mL of water. Drug should be taken 15-30 min after food intake including a fat component (like yogurt, milk, cheese or sausage).

Following first drug administration in Part A, evening and morning dose should be taken with a 12 h time interval (e.g. 20:00 h and 08:00 h) approximately at the same time each day during the treatment phase, within a time window of +/- 1 hour. In Part B, the once-daily dose should be taken approximately at the same time each morning during the treatment phase. Missed dose(s) will not be replaced.

As an exemption, at Visit 3 and Visit 6, drug administration will happen at the site outside the normal schedule for practical reasons to accomplish assessments. Patients will then return to their usual evening/morning interval (Part A) or thertheir usual morning interval (Part B), respectively.

All patients will be dispensed the trial medication consisting in total of 7 medication kits. Dispensing will be done during the trial stepwise via the IRT system at Visit 3, Visit 5, Visit 6 and Visit 8. During the above-mentioned visits, 1 medication kit will be assigned by the IRT system. At Visit 6 and Visit 8, 2 kits will be dispensed to cover the 4 weeks duration until EoT visit. In addition, a patient will receive 1 kit as a reserve at Visit 3 in case medication gets lost or the patients comes back to the next visit after more than 2 or 4 weeks, respectively.

The kits will be used for treating the patient at visits at the site and at the respective time points at home in between site vists.

During the COVID-19 pandemic, physical visits to the sites may need to be cancelled to ensure patient safety. Based on a thorough assessment of the benefits and risks, the investigator may still decide to continue the trial treatment, and trial medication may be shipped to the patient's home if acceptable according to local laws and regulations (for more details see Section 6.1).

4.1.5 Blinding and procedures for unblinding

4.1.5.1 Blinding

The table below summarizes the masking /blinding level of individual functions involved in the trial.

Role/function	Timing of unblinding/receiving access to the treatment information (including rationale)
Patients	Blinded until data ready for final analysis.
Investigator/Site Staff	Blinded until data ready for final analysis.
Sponsor (incl. clinical trial/project team), and database	After individual patient has been allocated to treatment. Periodic safety review and descriptive analyses of selected PK and PD endpoints will be performed during the trial conduct (see Section 7.2.7). The release of the treatment information at the individual time points will be documented accordingly.
Bioanalytical Staff	As requested for analysis of bioanalytical samples.

Table 4.1.5.1: 1	Blinding of functions involved in the tria	1
------------------	--	---

During the time a role/function is blinded, the randomisation schemes and medication kit lists (i.e. the treatment information) are kept restricted by the global Randomisation Team (gRT) per Sponsor Standard Operating Procedure (SOP).

4.1.5.2 Unblinding and breaking the code

Emergency unblinding will be available to the investigator via IRT. It must only be used in an emergency situation when the identity of the trial drug must be known to the investigator in order to provide appropriate medical treatment or otherwise assure safety of trial participants. The reason for unblinding must be documented in the source documents and/or appropriate eCRF page.

Due to the requirements to report Suspected Unexpected Serious Adverse Reactions (SUSARs), it may be necessary for a representative from BI's Pharmacovigilance group to access the randomisation code for individual patients during trial conduct. The access to the code will only be given to authorised Pharmacovigilance representatives for processing in the PV database system and not be shared further.

Prior to completion of treatment allocation in each trial part, an in dividual patient unblinding by the sponsor may occur, in case during the periodic safety review an AESI or any other relevant AE has occurred, that needs a more detailed investigation and is crucial for continuation or modification of the trial.

4.1.6 Packaging, labelling, and re-supply

The investigational medicinal products will be provided by BI or a designated Clinical Research Organization (CRO). They will be packaged and labelled in accordance with the principles of Good Manufacturing Practice (GMP). Re-supply to the sites will be managed via an IRT system, which will also monitor expiry dates of supplies available at the sites.

For details of packaging and the description of the label, refer to the ISF.

Proprietary confidential information © 2021 Boehringer Ingelheim International GmbH or one or more of its affiliated companies

4.1.7 Storage conditions

Drug supplies will be kept in their original packaging and in a secure limited access storage area according to the recommended storage conditions on the medication label. A temperature log must be maintained for documentation.

If the storage conditions are found to be outside the specified range, the Clinical Research Associate (CRA) (as provided in the list of contacts) must be contacted immediately.

4.1.8 Drug accountability

The investigator or designee will receive the investigational drugs delivered by the sponsor when the following requirements are fulfilled:

- Approval of the clinical trial protocol by the IRB / ethics committee
- Availability of a signed and dated clinical trial contract between the sponsor and the investigational site
- Approval/notification of the regulatory authority, e.g. competent authority
- Availability of the curriculum vitae of the Principal Investigator
- Availability of a signed and dated clinical trial protocol

Investigational drugs are not allowed to be used outside the context of this protocol. They must not be forwarded to other investigators or clinics. Patients should be instructed to return unused investigational drug.

The investigator or designee must maintain records of the product's delivery to the trial site, the inventory at the site, the use by each patient, and the return to the sponsor or warehouse / drug distribution centre or alternative disposal of unused products. If applicable, the sponsor or warehouse / drug distribution centre will maintain records of the disposal.

These records will include dates, quantities, batch / serial numbers, expiry ('use- by') dates, and the unique code numbers assigned to the investigational medicinal product and trial patients. The investigator or designee will maintain records that document adequately that the patients were provided the doses specified by the Clinical Trial Protocol (CTP) and reconcile all investigational medicinal products received from the sponsor. At the time of return to the sponsor <and/or> appointed CRO, the investigator or designee must verify that all unused or partially used drug supplies have been returned by the clinical trial patient and that no remaining supplies are in the investigator's possession.

4.2 OTHER TREATMENTS, EMERGENCY PROCEDURES, RESTRICTIONS

4.2.1 Other treatments and emergency procedures

There are no special emergency procedures to be followed.

4.2.2 Restrictions

4.2.2.1 Restrictions regarding concomitant treatment

All concomitant therapies will be recorded (including time of intake on study days) on the appropriate pages of the eCRF.

The use of certain medications, e.g. listed under the exclusion criteria (Section 3.3.3) is restricted during the trial. Details with regard to its use are provided in the ISF.

Drugs that are strong inhibitors of CYP3A4 have to be avoided for Part B, since a modest effect of the strong CYP3A4 inhibitor itraconazole on the PK of BI 1323495 in UGT2B17 EMs has been observed (see Section 1.2.3.1).

Excluded concomitant medications that might be of relevance in the population of this trial are provided in the ISF, including a detailed list of strong CYP3A4 inhibitors.

If treated with bronchodilators, wash-out of 24 hours for qd long acting, 12 hours for bid long acting, and 8 hours for short acting bronchodilators should be observed before pulmonary function tests.

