In the food effect trial 1405-0007, administration of 100 mg BI 1323495 together with a high-fat, high-calorie meal increased the exposure 2.4-fold and 1.7-fold based on C_{max} and AUC, respectively, versus fasted conditions. The maximum plasma concentrations were reached earlier in the fed state (median timepoint of maximum plasma concentration (t_{max}) 2.00) as compared to the fasted state (median t_{max} 3.52 h). The food effect was not different in poor metabolizers as compared to extensive metabolizers.

Boehringer Ingelheim		22 Apr 2021
BI Trial No.: 1405-0008		
c31693972-02	Clinical Trial Protocol	Page 28 of 111

The DDI trial 1405-0009 investigated the effects of multiple doses of itraconazole – a strong CYP3A4 and P-gp inhibitor – on the relative bioavailability of a single dose of 10 mg BI 1323495 in EMs. Itraconazole caused a modest increase in exposure to BI 1323495 in gMean AUC_{0- ∞} and C_{max} of ~1.7-fold and ~1.4-fold, respectively. Therefore, concomitant treatment with strong CYP3A4 / P-gp inhibitors should be avoided in EMs. In PMs, the effect of CYP3A4 / P-gp inhibition has not yet been assessed.

In a DDI trial (1405-0015) the effects of a single dose of 300 mg BI 1323495 on the PK of Rosuvastatin (10 mg) and Dabigatran (75 mg) were tested in 14 healthy subjects each. Rosuvastatin is a sensitive substrate of BCRP and OATP1B1, while Dabigatran is a sensitive substrate for P-gp. Co-administration with BI 1323495 increased the C_{max} (1.14-fold) and AUC (1.05-fold) of Rosuvastatin only slightly, with the upper boundary of the 90% confidence interval (CI) within or only slightly above (Cmax) above 125%. Co-administration with BI 1323495 increased the AUC (1.09-fold) and Cmax (1.08-fold) of dabigatran only slightly with the upper boundary of the 90% CI still within 125%. Hence, BI 1323495 appears not to have a clinically relevant effect on BCRP, OATP1B1 and P-gp (c33366190-01).

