3.2 DISCUSSION OF TRIAL DESIGN, INCLUDING THE CHOICE OF CONTROL GROUP(S)

Since this trial evaluates BI 1323495 for 12 weeks (compared to 10.5 days – for bid dose groups, or 11 days – for the qd dose group in the healthy volunteer MRD trial) and for the first time in a patient population up to a higher age, safety and tolerability is the recommended primary objective for assessing a new drug in patients with nCFB. Due to its mechanism of action, a 12-week treatment period is considered sufficient to evaluate the PK and PD, and to potentially obtain an early sign of clinical efficacy of BI 1323495. A 2-week follow-up period without treatment is considered to be sufficient, as this covers twice the residual effect period during which BI 1323495 exposures are expected to return to not quantifiable levels and pharmacodynamic effects (inhibition of NE) are expected to have fully reversed.

Each trial part has a parallel-group, randomised, double-blind and placebo-controlled design as this is considered the most appropriate design to assess safety and efficacy of different doses of BI 1323495. In this trial, a double-blind (patient and investigator blinded, sponsor unblinded - for details refer to Section 4.1.5) concept was chosen to reduce the bias with regard to treatment-dependent effects as much as possible. Due to a close safety monitoring, this approach is considered acceptable for patients. A placebo group is included in order to control for safety, tolerability, and pharmacodynamic effects of the trial medication.

Only UGT2B17 extensive metabolizers will be included in this study to reduce PK variability. A dose of 30 mg bid BI 1323495 has been shown to be safely tolerated and was associated with a median level of >90% inhibition of NE at trough in blood of a healthy volunteer population of UGT2B17 EMs. Of note, in addition, according to preliminary pharmacometric simulations, a dose of 30 mg bid is predicted to remain within the exposure boundaries defined based on the results of the non-clinical toxicity studies even in UGT2B17 PMs who are expected to have BI 1323495 exposures exceeding those in EMs. Therefore, this dose level might be compatible later in clinical development with a mixed population of both PMs and EMs (beyond the scope of this trial). As such, this dose could be a therapeutic dose for EMs and PMs alike.

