3.3.1 Main diagnosis for trial entry

The key in- and exclusion criteria were selected to allow the enrolment of the preferred target population, i.e., patients of a broad age range that have clinically stable nCF bronchiectasis with regular daily sputum production and detectable NE activity in sputum. Eligibility will be confirmed at screening and baseline. The screening for detectable NE activity is considered crucial to reduce the potentially high variability in regard to sputum NE activity and ensure a trial population in which a treatment response to NE inhibition can be expected [R19-3080].

Concomitant maintenance treatment for the management of nCFB is allowed, except for strong CYP 3A4 inhibitors (a specified list of not-allowed comedications will be provided in ISF).

Please refer to Section 8.3.1 (Source Documents) for the documentation requirements pertaining to the in- and exclusion criteria.

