- 9. Subjects genotyped as UGT2B17 extensive metabolizers prior to randomisation, i.e., carrying at least one functional allele of the UGT2B17 gene (*1/*1 or *1/*2).

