6.2 DETAILS OF TRIAL PROCEDURES AT SELECTED VISITS

6.2.1 Screening and run-in period

Screening Period

Boehringer Ingelheim		22 Apr 2021
BI Trial No.: 1405-0008		
c31693972-02	Clinical Trial Protocol	Page 76 of 111

After having been informed about the trial, all subjects will provide written informed consent in accordance with GCP and local legislation prior to enrolment in the study. At screening, the medical examination will include demographics, height and body weight, smoking and alcohol use, relevant medical history and concomitant therapy, review of inclusion and exclusion criteria, review of vital signs (BP, PR, aural body temperature), 12-lead ECG, pregnancy testing, laboratory tests (including UGT2B17 genotyping), sputum collection, lung function and a physical examination. For information regarding physical examination, vital signs, laboratory tests and ECG refer to Sections 5.2.1, 5.2.2, 5.2.3 and 5.2.4.

Genotyping for UGT2B17 will be performed in all trial patients (for details, see Section 5.4). The Screening Visit 1 can cover a period of up to 4 weeks, e.g. to wait for laboratory results, or if washout of certain restricted medication is required (see Section 4.2.2.1).

During the baseline period (Visits 2a, b and Visit 3 before treatment), patients have to donate two to three valid sputum samples.

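### Section 4.2.2.1 bars strong CYP3A4 inhibitors for Part B alone, although its stated reason covers both parts and sections 1.2.3.1 and 3.3.1 set no part limit

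*Protocol*

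**What the plan says.** Four places in the protocol bear on strong CYP3A4 inhibitors.

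- **Section 4.2.2.1** gives the operative rule: "Drugs that are strong inhibitors of CYP3A4 have to be avoided for Part B". The reason in the same sentence is a modest itraconazole effect on the drug's PK in UGT2B17 EMs, with a reference to 1.2.3.1. A further sentence says "Excluded concomitant medications that might be of relevance in the population of this trial are provided in the ISF", and adds that this includes a list of strong CYP3A4 inhibitors. Part A is not mentioned.
- **Section 1.2.3.1** draws the conclusion from the itraconazole trial: "concomitant treatment with strong CYP3A4 / P-gp inhibitors should be avoided in EMs". It sets no part or dose limit.
- **Section 3.3.1** says "Concomitant maintenance treatment for the management of nCFB is allowed, except for strong CYP 3A4 inhibitors", again with no part limit, and points to an ISF list.
- **Section 3.3.3, exclusion criterion 4** refers further excluded medication to the ISF, for the whole trial.

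The genotype rule is common to both parts. Inclusion criterion 9 requires "Subjects genotyped as UGT2B17 extensive metabolizers prior to randomisation", and section 3.2 explains why: "Only UGT2B17 extensive metabolizers will be included in this study to reduce PK variability".

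Two other rules refer to section 4.2.2 or 4.2.2.1. Section 6.2.1 allows up to 4 weeks of screening "if washout of certain restricted medication is required", citing 4.2.2.1. Section 3.3.4.1 deals with interfering co-medication during treatment, citing 4.2.2.

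**The concern.** The restriction is narrower than its own justification. A reason that concerns EMs cannot by itself separate Part A from Part B when both parts contain only EMs. A site reading 4.2.2.1 alone would take the rule to concern Part B. A site reading 1.2.3.1 or 3.3.1 would take it to concern everyone.

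The gap is widest for strong inhibitors that are not bronchiectasis maintenance treatment, such as a short course given for another condition. Section 3.3.1 speaks only of maintenance treatment, so for those drugs the operative text is 4.2.2.1 and whatever the ISF contains.

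At stake is added PK and PD variability in the 30 mg bid arm, which has 9 patients, in a trial that restricts genotype in order to limit that variability. A site could also fail to apply the screening washout to a Part A candidate, because 6.2.1 takes its restricted drugs from 4.2.2.1.

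**Working it through.** **Comparison of the texts**

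| Section | Who should avoid strong inhibitors | Part limit | Dose limit |
|---|---|---|---|
| 1.2.3.1 | EMs | none | none |
| 3.3.1 | patients on bronchiectasis maintenance treatment | none | none |
| 4.2.2.1 | Part B | Part B | none stated |

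Only 4.2.2.1 carries a part limit, and its stated reason does not supply one. The allowance in section 1.2.2.3 for doses up to 70 mg bid concerns sensitive substrates of CYP3A4, not inhibitors, so it does not explain the limit.

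**Patients outside the wording of 4.2.2.1.** Part A has 12 of the 36 patients: 9 on 30 mg bid and 3 on placebo (section 7.4, ratio 3:1). The interaction can alter exposure only in the 9.

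**Inputs for the size**
- 30 mg bid in EMs at steady state: AUC over the 12 h interval 475 nmol·h/L (gCV 86.2%), Cmax 64.4 nmol/L (Table 1.2.3.1: 1).
- Itraconazole effect: AUC about 1.7-fold, Cmax about 1.4-fold (section 1.2.3.1).
- Blood NE inhibition: IC50 3.6 nM, IC90 33 nM, IC95 69 nM, maximum 100% (section 1.2.3.2).
- Exposure caps: AUC0-24 11,500 nM·h, Cmax 1,900 nM (section 1.2.2.4).

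**Model check.** With inhibition = 100 × C/(C + 3.6), 33 nM gives 90.2% and 69 nM gives 95.0%. This reproduces the stated IC90 and IC95.

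**Effect in one affected patient**
- Average concentration without inhibitor: 475/12 = 39.6 nM, giving 91.7% inhibition.
- With inhibitor: 39.6 × 1.7 = 67.3 nM, giving 94.9%.
- Difference: about 3.3 points.

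**Effect on the arm.** The documents give no number of users. Each user among 9 moves the arm mean by 3.26/9 = 0.36 points, so the possible range is 0 (no users) to about 3.3 points (all 9).

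**Compared with existing PK spread.** The between-patient log-SD is √ln(1 + 0.862²) = 0.745, and ln 1.7 = 0.531. The shift is 0.531/0.745 = 0.71 of that SD.

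**Exposure caps**
- AUC0-24 = 2 × 475 × 1.7 = 1,615 nM·h, and 1,615/11,500 = 14% of the cap.
- Cmax = 64.4 × 1.4 = 90 nM, against a cap of 1,900 nM.

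**The case against.** **A dose-based exemption for Part A is pharmacologically plausible.** Section 3.2 predicts that 30 mg bid stays within the exposure boundaries even in poor metabolizers. Their AUC at that dose is 2,380 per interval, or 4,760 nM·h per day, well above the 1,615 computed for an inhibited EM. The amendment log lists 4.2.2 among the sections updated to support 150 mg qd, so the Part B limit may be deliberate. That stands as pharmacology. But the protocol does not give this reason, and an exemption would still conflict with 1.2.3.1 and 3.3.1. If one is intended, all three sections need changing.

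**A reader might infer that Part A patients are free to take these drugs.** The documents do not support that. Silence on Part A is not permission. Section 3.3.1 bars them as maintenance treatment, exclusion criterion 4 ties ISF-listed drugs to eligibility, and the ISF list is described for the population of the trial without a part limit. What remains is a conflict between instructions, whose extent depends on a list that is not available.

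**A reader might also infer that the SAP exclusion rules fail.** SAP 6.6.2 and 6.6.3 drop biomarker and spirometry data from first use of restricted medications and do not define that term by part. This is missing detail with a process behind it. Cases are identified at quality monitoring meetings and recorded as important deviations. SAP 7.2 sets the report planning meeting as the latest point for judging the relevance of concomitant therapy. For use during treatment, protocol 3.3.4.1 says it will be "decided on a case-by-case basis after consultation with the Sponsor whether or not discontinuation of trial treatment is required".

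**The effect is small and hypothetical.** This stands. The 3-point shift is no larger than the observed difference between trough and post-dose medians at 30 mg bid, 91.8% and 95.1% (Table 1.2.3.2: 1). Exclusion of active allergic bronchopulmonary aspergillosis, defined partly by antifungal treatment, also removes one likely source of itraconazole-type use.

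**Conclusion.** The inconsistency is real and should be corrected. Section 4.2.2.1 limits to Part B a precaution whose stated reason applies to both parts, and two other sections state the precaution without that limit. The conflict mainly affects strong inhibitors used in Part A for something other than bronchiectasis maintenance.

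The consequence is minor: about 3 points of modelled blood NE inhibition per affected patient on 30 mg bid, with an unknown number of such patients. It would show as extra PK and PD variability in that arm. There is no exposure-cap concern, since AUC0-24 would be about 14% of the cap. The SAP exclusion rules cover biomarkers and spirometry, so they do not affect the primary endpoint.

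The size rests on these assumptions:
- The 1.7-fold figure comes from single-dose data and is taken to hold at steady state. The protocol gives the dose in that trial as 10 mg in section 1.2.3.1 and 100 mg in section 1.2.3.3, and exposure is not dose-proportional.
- The inhibition model is for blood, not sputum, and is evaluated at the average concentration from geometric-mean exposure.
- The ISF list has not been seen. If it bars these drugs in both parts, much of the practical gap closes, although the protocol wording would still disagree with itself.

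**What to change.** In section 4.2.2.1, delete the two words that limit the rule to Part B (three with the preposition), so that strong CYP3A4 inhibitors are to be avoided throughout the trial, as 1.2.3.1 and 3.3.1 already say. Confirm that the ISF list of strong inhibitors applies to both parts.

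The cost is a few words in the protocol and one check of the ISF. A Part A candidate taking such a drug must stop it or not enter. Section 3.3.1 already requires this for maintenance treatment, and section 6.2.1 already allows up to 4 weeks of screening for washout.

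No SAP change is part of this fix. What counts as a restricted medication there is a matter of detail that can be settled in the deviation specifications.
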